- Abortuses N
- Impaired Decision Making Capacity N
- Cancer Subjects N
- Laboratory Personnel N
- Healthy Volunteers N
- Students N
- Employees N
- Prisoners N
- Other (i.e., any population that is not specified above) Y

Study Location(s) Checklist

Yes/No

- Stanford University
 - Clinical & Translational Research Unit (CTRU)
 - Stanford Hospital and Clinics
 - Lucile Packard Children's Hospital (LPCH)
 - VAPAHCS (Specify PI at VA) Y
- [name]
- Other (Click ADD to specify details)

General Checklist

Multi-site

Yes/No

- Is this a multi-site study? A multi-site study is generally a study that involves one or more medical or research institutions in which one site takes a lead role.(e.g., multi-site clinical trial) N

Collaborating Institution(s)

Yes/No

Title: The Impact of CBT-I on Cannabis Cessation Outcomes

Approval Period: 03/27/2015 - 03/11/2016

- Are there any collaborating institution(s)? A collaborating institution is generally an institution that collaborates equally on a research endeavor with one or more institutions. N

Cancer Institute

Yes/No

- Cancer-Related Studies (studies with cancer endpoints), Cancer Subjects (e.g., clinical trials, behavior/prevention) or Cancer Specimens (e.g., blood, tissue, cells, body fluids with a scientific hypothesis stated in the protocol). N

Drug /Device

Yes/No

- Investigational drugs, biologics, reagents, or chemicals? N
- Commercially available drugs, reagents, or other chemicals administered to subjects (even if they are not being studied)? N
- Investigational Device / Commercial Device used off-label? N
- IDE Exempt Device (Commercial Device used according to label, Investigational In Vitro Device or Assay, or Consumer Preference/Modifications/Combinations of Approved Devices) Y
- Protocol involves studying potentially addicting drugs? N

Clinical Trials

Yes/No

- Click "yes" to confirm that you have accessed the website and read the clinicaltrials.gov reporting requirements provided. Y
- This study will be registered on clinicaltrials.gov? Y

Tissues and Specimens

Yes/No

- Human blood, cells, tissues, or body fluids (tissues)? N
- Tissues to be stored for future research projects? N
- Tissues to be sent out of this institution as part of a research agreement? For guidelines, please see <http://stanford.edu/group/ICO/researcher/reMTA.html>
<http://stanford.edu/group/ICO/researcher/reMTA.html> N

Biosafety (APB)

Yes/No

- Are you submitting a Human Gene Transfer investigation using biological agent or recombinant DNA vector? If yes, please complete and attach the Gene Transfer Protocol N

Title: The Impact of CBT-I on Cannabis Cessation Outcomes
Approval Period: 03/27/2015 - 03/11/2016

Application Supplemental Questions to section 16 of the eProtocol application.

- Are you submitting a Human study using biohazardous/infectious agents? If yes, refer to the <http://www.stanford.edu/dept/EHS/prod/researchlab/bio/index.html> Administrative Panel on BioSafety website prior to performing studies. N
- Are you submitting a Human study using samples from subjects that contain biohazardous/infectious agents? If yes, refer to the <https://ehsappprd1.stanford.edu/eprbio/> Administrative Panel on BioSafety website prior to performing studies. N

Human Embryos or Stem Cells

Yes/No

- Human Embryos or gametes? N
- Human Stem Cells (including hESC, iPSC, cancer stem cells, progenitor cells). N

Veterans Affairs (VA)

Yes/No

- The research recruits participants at the Veterans Affairs Palo Alto Health Care System(VAPAHCS). Y
- The research involves the use of VAPAHCS non-public information to identify or contact human research participants or prospective subjects or to use such data for research purposes. Y
- The research is sponsored (i.e., funded) by VAPAHCS. Y
- The research is conducted by or under the direction of any employee or agent of VAPAHCS (full- time, part-time, intermittent, consultant, without compensation (WOC), on-station fee-basis, on- station contract, or on-station sharing agreement basis) in connection with her/his VAPAHCS responsibilities. Y
- The research is conducted using any property or facility of VAPAHCS. Y

Equipment

Yes/No

- Use of Patient related equipment? If Yes, equipment must meet the standards established by Hospital Instrumentation and Electrical Safety Committee [contact]) N
- Medical equipment used for human patients/subjects also used on animals? N
- Radioisotopes/radiation-producing machines, even if standard of care? http://www.stanford.edu/dept/EHS/prod/researchlab/radlaser/Human_use_guide.pdf More Info N

Payment

Yes/No

- Subjects will be paid for participation? See payment considerations. Y

Title: The Impact of CBT-I on Cannabis Cessation Outcomes
Approval Period: 03/27/2015 - 03/11/2016

Funding	Yes/No
• Training Grant?	Y
• Program Project Grant?	N
• Federally Sponsored Project?	N
• Industry Sponsored Clinical Trial?	N

Funding

Funding - Grants/Contracts	
Funding Administered By: VA	SPO # (if available):
Grant # (if available): CX001023	Funded By (include pending): VA
Principal Investigator: [name]	
Grant/Contract Title if different from Protocol Title:	
Y	For Federal projects, are contents of this protocol the same as described in Federal proposal application?
N	Is this a Multiple Project Protocol (MPP)?
N	Is this protocol under a MPP?

Funding - Fellowships

Gift Funding

Dept. Funding

Other Funding

Resources:

- a) **Qualified staff.**

Please state and justify the number and qualifications of your study staff.

We have a diverse and highly qualified staff with expertise in the specific duties that they will perform in the research project. This includes expertise in statistics and assessment methodology, clinical psychology, human subjects research, project management, and interview assessment of vulnerable community-based populations, as proven by clinical and scientific training or previous experience.

- b) **Training.**

Describe the training you will provide to ensure that all persons assisting with the research are

Title: The Impact of CBT-I on Cannabis Cessation Outcomes
Approval Period: 03/27/2015 - 03/11/2016

informed about the protocol and their research-related duties and functions.

All members of the study team have been involved in the development of the protocol, and we will have team meetings both prior to study start and periodically during the study period to assure that all staff understand their role in the study and the functions that they must perform. Additionally, [name] will meet with all staff weekly to discuss research related duties and progress

c) Facilities.

Please describe and justify.

Evaluation and groups will be conducted within the National Center for PTSD on the Menlo Park campus. This facility includes a secure servers where data will be stored and maintained by VA IRMS. We have secure phone and computer resources to conduct the study.

d) Sufficient time.

Explain whether you will have sufficient time to conduct and complete the research. Include how much time is required.

We will have sufficient time to conduct and complete the research. All study team members have devoted sufficient time to the project to complete the tasks required of them. We will require 5 years to complete the study, with the majority of the time intensive work being conducted by the PI.

e) Access to target population.

Explain and justify whether you will have access to a population that will allow recruitment of the required number of participants.

We will have access to over 700 qualified patients at VAPAHCS and hope to recruit approximately 168 participants. As the study involves only completion of questionnaires, home-based actigraphy sleep assessments, and a behavioral intervention group, with participants being reimbursed of their time, we should have no difficulty recruiting 168 participants.

f) Access to resources if needed as a consequence of the research.

State whether you have medical or psychological resources available that participants might require as a consequence of the research when applicable. Please describe these resources.

The study consists of questionnaires, home-based actigraphy sleep assessments, and a 6-session behavioral intervention. We have multiple clinical psychologists on the study staff who will be available to assist should any problems occur in conjunction with the study.

g) Lead Investigator or Coordinating Institution in Multi-site Study.

Please explain (i) your role in coordinating the studies, (ii) procedures for routine communication with other sites, (iii) documentation of routine communications with other sites, (iv) planned management of communication of adverse outcomes, unexpected problems involving risk to participants or others, protocol modifications or interim findings.

1. Purpose

Title: The Impact of CBT-I on Cannabis Cessation Outcomes
Approval Period: 03/27/2015 - 03/11/2016

a) In layperson's language state the purpose of the study in 3-5 sentences.

The proposed study will employ a novel, multi-method approach to investigate the efficacy of group-based cognitive behavioral therapy for insomnia (CBT-I), and the incremental benefit provided by an adjunctive sleep mobile app, in improving cannabis outcomes among 168 cannabis dependent Veterans.

b) State what the Investigator(s) hope to learn from the study. Include an assessment of the importance of this new knowledge.

Information from this study can be directly applied to improve SUD treatment among Veterans by targeting sleep disturbances in order to reduce rates of lapse/relapse and improve outcomes. Improved outcomes from SUD treatment can help reduce recidivism, allowing for resources to be allocated to new incidences of SUDs, and reduce wait times to receive services. Finally, these data can be used to influence policy, with the ultimate goal of increasing the efficacy, and value of SUD treatment.

c) Explain why human subjects must be used for this project. (i.e. purpose of study is to test efficacy of investigational device in individuals with specific condition; purpose of study is to examine specific behavioral traits in humans in classroom or other environment)

The purpose of the study is to test the efficacy of a behavioral sleep intervention (with mobile app) among individuals with cannabis use disorder.

2. Study Procedures

a) Please SUMMARIZE the research procedures, screening through closeout, which the human subject will undergo. Refer to sections in the protocol attached in section 16, BUT do not copy the clinical protocol. Be clear on what is to be done for research and what is part of standard of care.

The proposed study will employ a between subjects prospective design to follow 168 Veterans with CUD and co-occurring insomnia over the course of six months while individuals complete a treatment/placebo group within the context of outpatient addiction treatment at the Menlo Park division of the VA Palo Alto Health Care System. Overall, this design will involve assessments during the following times: baseline (prior to the intervention), over the course of the intervention, upon completion of the treatment/placebo group conducted during week 6 (completion of the sleep [or placebo] intervention), and three follow-up assessments conducted 2-weeks, 4-weeks, and 6-months post-treatment. Veterans will be recruited through the outpatient substance abuse treatment program within the Menlo Park Division of the VA Palo Alto Health Care System and through fliers placed throughout the community. Interested participants will complete a brief phone-based screening with a trained research assistant to assess for initial inclusionary/exclusionary criteria. Eligible individuals will then be scheduled for a baseline assessment once enough individuals have been recruited to comprise three groups for the treatment/placebo group portion. Baseline assessments will consist of structured clinical interviews, questionnaires, and a urine toxicology to assess for the presence/absence of marijuana. Eligible participants will then be randomly assigned to one of three conditions: (1) CBT-I with adjunctive sleep mobile app (CBT-I-MA); (2) CBT-I only (CBT-I); or (3) Placebo-control(PC). The treatment/placebo groups will occur weekly for six consecutive weeks. During this time, substance use (including

Title: The Impact of CBT-I on Cannabis Cessation Outcomes
Approval Period: 03/27/2015 - 03/11/2016

cannabis) and sleep will be monitored. Upon completion of the treatment/placebo group (week 6), individuals will complete self-report questionnaires and a home-based actigraphy sleep assessment. Follow-up assessment will then occur Two-weeks, 4-weeks, and 6-months post-treatment (follow-up assessments). Participants will complete home-based sleep assessments (actigraphy) and the same self-report and interview-based questionnaires that were administered during baseline as well as a urine toxicology to assess for the presence/absence of marijuana. Assessments will be completed in person. Baseline and 6-month follow-up interviews and questionnaires will take 3 hours to complete, while 2-week and 4-week post-treatment follow-up appointments will take 1 hour. Home-based sleep assessments will occur overnight for the length of each individual's typical sleep cycle (approximately 8 hours).

b) Explain how the above research procedures are the least risky that can be performed consistent with sound research design.

The primary risk of the current study involves confidentiality of data. Here, we have taken data security precautions that reduce this risk, including keeping all data on a secure server with study data separated from participant contact information. To reduce clinical risk, we have experienced clinical staff on the project, including clinical psychologists who are experts in and experienced with assessment of patients for substance use disorders and sleep disorders within the context of the VA. They will be available to assist if any clinical issues arise during the patient interview.

c) State if deception will be used. If so, provide the rationale and describe debriefing procedures. Since you will not be fully informing the participant in your consent process and form, complete an alteration of consent (in section 13). Submit a debriefing script (in section 16).

Deception is not used in this protocol.

d) State if audio or video recording will occur. Describe what will become of the recording after use, e.g., shown at scientific meetings, erased. Describe the final disposition of the recordings.

Interviews will be audio-taped and the reliability of a random selection of 20% will be determined and checked for accuracy by [name]. Audiotapes will be maintained in compliance with VA guidelines, and stored in locked cabinets during the study itself.

e) Describe alternative procedures or courses of treatment, if any, that might be advantageous to the participant. Describe potential risks and benefits associated with these. Any standard treatment that is being withheld must be disclosed in the consent process and form. (i.e. standard-of-care drug, different interventional procedure, no procedure or treatment, palliative care, other research studies).

The alternative is not to participate in the study. As there is no formal intervention component to the current study, there is no alternative treatment course for those who do, versus those who do not, participate in the study. All participants will have access to substance use treatment within VA, consistent with treatment guidelines.

f) Will it be possible to continue the more (most) appropriate therapy for the participant(s) after the conclusion of the study?

The outpatient SUD treatment program is currently available at the VA Palo Alto. Thus, patients can utilize it at any time. The VAPAHCS also offers cognitive behavioral therapy for insomnia which can be accessed by veterans.

g) Study Endpoint. What are the guidelines or end points by which you can evaluate the different treatments (i.e. study drug, device, procedure) during the study? If one proves to be clearly more effective than another (or others) during the course of a study, will the study be terminated before the projected total participant population has been enrolled? When will the study end if no important differences are detected?

Title: The Impact of CBT-I on Cannabis Cessation Outcomes
Approval Period: 03/27/2015 - 03/11/2016

N/A.

3. Background

a) Describe past experimental and/or clinical findings leading to the formulation of the study.

The Prevalence of cannabis use disorder (CUD) has been steadily increasing within the Veteran Health Administration (VHA), along with the related significant physical, cognitive, and psychological sequelae. Even in patients with a strong motivation to quit and the presence of empirically-supported interventions (Roffman & Stephens, 2006), Veterans who receive treatment for CUD have high rates of lapse (63% by 6-months post-treatment) and relapse (71% within 6-months post-treatment; Moore et al., 2003). Thus, identifying strategies to improve response to CUD treatment is in the interest of all VHA stakeholders.

Disturbed sleep is common among individuals with CUD and has been shown to result in increased rates of lapse/relapse to cannabis ([name] et al., 2012). In fact, 48%-77% of individuals making a cannabis cessation attempt report lapsing/relapsing specifically to manage poor sleep (Copersino et al., 2000; Levin et al., 2010). Therefore, when individuals with poor sleep attempt to quit using cannabis, not only is their coping mechanism removed, but they are also likely to experience withdrawal-related sleep difficulties, increasing risk for lapse/relapse. Providing a behavioral sleep intervention within the context of CUD treatment, has the potential to improve these cessation outcomes.

Cognitive behavioral therapy for insomnia (CBT-I) is a well-established first-line treatment for insomnia. While CBT-I is being disseminated throughout VHA, it is rarely received by Veterans with substance use disorders (SUDs) and, among those that do receive it, it is almost always delivered following a cessation attempt. While CBT-I has been shown to be an effective treatment for improving sleep among individuals with insomnia and co-occurring conditions, including SUDs, there has yet to be an investigation of the impact of providing CBT-I prior to CUD treatment with the goal of improving cessation outcomes. In addition, the development of an adjunct behavioral intervention delivered via mobile app technology within VA holds great promise to bolster CBT-I outcomes, however, such an approach has yet to be evaluated.

b) Describe any animal experimentation and findings leading to the formulation of the study.

N/A

4. Radioisotopes or Radiation Machines

**a) List all standard of care procedures using ionizing radiation (radiation dose received by a subject that is considered part of their normal medical care). List all research procedures using ionizing radiation (procedures performed due to participation in this study that is not considered part of their normal medical care). List each potential procedure in the sequence that it would normally occur during the entire study. http://www.stanford.edu/dept/EHS/prod/researchlab/radlaser/Human_use_guide.pdf
More Info**

Identify Week/Month of study	Name of Exam	Identify if SOC or Research
------------------------------	--------------	-----------------------------

b) For research radioisotope projects, provide the following radiation-related information:

Title: The Impact of CBT-I on Cannabis Cessation Outcomes
Approval Period: 03/27/2015 - 03/11/2016

Identify the radionuclide (s) and chemical form (s).

For the typical subject, provide the total number of times the radioisotope and activity will be administered (mCi) and the route of administration.

If not FDA approved provide dosimetry information and reference the source documents (package insert, MIRD calculation, peer reviewed literature).

- c) For research radiation machine projects, provide the following diagnostic procedures:

For well-established radiographic procedures describe the exam.

For the typical subject, identify the total number of times each will be performed on a single research subject.

For each radiographic procedure, provide the setup and technique sufficient to permit research subject dose modeling. The chief technologist can usually provide this information.

For radiographic procedures not well-established, provide FDA status of the machine, and information sufficient to permit research subject dose modeling.

- d) For research radiation machine projects, provide the following therapeutic procedures:

For a well-established therapeutic procedure, identify the area treated, dose per fraction and number of fractions. State whether the therapeutic procedure is being performed as a normal part of clinical management for the research participants's medical condition or whether it is being performed because the research participant is participating in this project.

For a therapeutic procedure that is not well-established, provide FDA status of the machine, basis for dosimetry, area treated, dose per fraction and number of fractions.

5. Devices

- a) Please list in the table below all Investigational Devices (including Commercial Devices used off-label) to be used on participants.
- b) Please list in the table below all IDE Exempt Devices (Commercial Device used according to label, Investigational In Vitro Device or Assay, or Consumer Preference/Modifications/Combinations of Approved Devices) to be used on participants.

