5.1 Device Name: CBT-I mobile app

Describe the device to be used.

CBT-I mobile application for smartphone

Manufacturer

IDE Exemption

Y This is a legally marketed device being used in accordance with its labeling.

Title: The Impact of CBT-I on Cannabis Cessation Outcomes
Approval Period: 03/27/2015 - 03/11/2016

6. Drugs, Reagents, or Chemicals

- a) Please list in the table below all investigational drugs, reagents or chemicals to be administered to participants.
- b) Please list in the table below all commercial drugs, reagents or chemicals to be administered to participants.

7. Medical Equipment for Human Subjects and Laboratory Animals

If medical equipment used for human patients/participants is also used on animals, describe such equipment and disinfection procedures.

N/A.

8. Participant Population

- a) State the following: (i) the number of participants expected to be enrolled at Stanford-affiliated site(s); (ii) the total number of participants expected to enroll at all sites; (iii) the type of participants (i.e. students, patients with certain cancer, patients with certain cardiac condition) and the reasons for using such participants.

In this study, we focus on a sample of 168 male and female cannabis dependent adult veterans with sleep disturbances. These subjects will be used because we are testing the impact of a behavioral sleep program (with mobile app) on cannabis use.

- b) State the age range, gender, and ethnic background of the participant population being recruited.

Subjects will range in age from 18-90, with most subjects in the 35-65 age range that is currently overrepresented in VA programs. We expect over 90% of participants will be male. We also expect a diverse representation of ethnic backgrounds, in proportion to the ethnic breakdown at the participating VA health care system. The program director estimates that the outpatient population treated at the clinic is 60% black, 20% white, 10% Hispanic and 10% other races.

- c) State the number and rationale for involvement of potentially vulnerable subjects in the study (including children, pregnant women, economically and educationally disadvantaged, decisionally impaired, homeless people, employees and students). Specify the measures being taken to minimize the risks and the chance of harm to the potentially vulnerable subjects and the additional safeguards that have been included in the protocol to protect their rights and welfare.

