(7) We will provide staff within veterans programs forms which they will distribute to individuals within their program. The forms will inquire if individuals are interested in hearing more about potential options for participating in research. They will be asked to check yes or no regarding their interest and provide their name and contact information. Study staff will collect the forms from the staff once/week and will contact those individuals indicating they were interested in research participation. This form can be found in section 16.

Patients interested in the study will contact the research laboratory to complete a brief phone screening for initial eligibility criteria and schedule a baseline appointment.

h) Inclusion and Exclusion Criteria.

Identify inclusion criteria.

To be included in the current study individuals must (1) be a Veteran 18 years or older; (2) meet DSM-5 diagnostic criteria for cannabis use disorder; and (3) meet DSM-5 diagnostic criteria for insomnia.

Identify exclusion criteria.

Individuals will be excluded based on evidence of the following: (1) inability to provide fully-informed written consent to participate; (2) history of, or current, psychotic symptoms or bipolar disorder; (3) current pregnancy; (4) sleep apnea as indicated by a score ≥ 5 on the STOP-Bang assessment; and (5) active suicidal/homicidal intent.

i) Describe your screening procedures, including how qualifying laboratory values will be obtained. If you are collecting personal health information prior to enrollment (e.g., telephone screening), please request a waiver of authorization for recruitment (in section 15).

Participants calling the laboratory with interest in the study will be briefly screened over the telephone to determine if they are likely to be study eligible. Likely eligible participants will be enrolled in the study and assessed for presence of cannabis use disorder, using the structured clinical interview for DSM-5, and insomnia (using the insomnia severity index). Participants who are positive for cannabis use disorder and insomnia, will be included in the study. Participants who are negative for cannabis use disorder or insomnia, will end study participation at this point.

j) Describe how you will be cognizant of other protocols in which participants might be enrolled. Please explain if participants will be enrolled in more than one study.

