We will implement a multi-pronged recruitment process. First, we will advertise the study to each Veteran presenting to the outpatient SUD treatment center at VAPAHCS. Second, staff within the outpatient SUD treatment center will provide study and contact information to patients beginning the program. Finally, in order to ensure enrollment of individuals with comorbid insomnia, we will also advertise within the outpatient SUD treatment center with flyers that specifically mention insomnia symptoms. Patients interested in the study will contact the research laboratory to complete a brief phone screening for initial eligibility criteria and schedule a baseline appointment. Several mentors including Drs. [name] and [name] have long-standing relationships with the outpatient SUD treatment center at the VAPAHCS which will facilitate recruitment and completion of this project (Also see letter from [name]).

2a.3.d. Participants.

A sample of 187 male and female (10%) Veterans with CUD and insomnia, self-motivated to make a cannabis quit attempt within the context of the VA outpatient SUD treatment center at the Menlo Park Division of the VA Palo Alto Health Care System, will be targeted. Allowing for 10% attrition during the baseline assessment, a sample of 187 will provide a final randomization of 168 Veterans into one of the three treatment conditions. In FY 2011, the outpatient SUD program at the VAPAHCS treated approximately 485 unique individuals meeting criteria for CUD. Based on previous research, we expect that approximately 60% of individuals with a CUD will also meet criteria for insomnia (Budney et al., 2008). Therefore, this sample will be feasible to recruit by the beginning of year 4 (see “Timeline for Primary and Secondary Research Activities”).

2a.3.e. Inclusionary and Exclusionary Criteria.

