Therefore a total sample of 168 will be adequate to detect all expected effects. An intent-to-treat approach will also be used. Therefore, all individuals randomized will be included in analyses. In the event that a set of individuals do not receive a minimum intervention dose (i.e., attend 70% of group sessions; Litt et al., 2007; Project Match Research Group, 1997), we will conduct analyses with and without these individuals. This sample size is feasible over the course of 4 years as evidenced in previous work conducted among outpatient substance use research protocols (Heinz et al., 2013).

Missing Data. Based on our protocol to limit participant attrition, we expect relatively little missing data over the 6 months of this study. We will limit the effect of missing data both methodologically and statistically. *First, we will account for 10% loss prior to randomization. Therefore, we will aim to recruit 187 individuals, with the goal of randomizing 168 individuals for the intent-to-treat analyses. Second, we chose to model our data using a GLMM approach as this method allows for multiple missing data points within longitudinal designs making this a robust analytic method for handling missing data. Additionally, as it is likely that not all participants will be included in analyses due to missing data, we will examine the reliability of the results by re-conducting analyses on complete data sets obtained through multiple imputation procedures and pooling*

results (Graham, 2012). Sensitivity analysis will then be conducted to examine the impact of missing data on outcomes (Carpenter et al., 2007).

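### The protocol gives 168 both as the number to recruit and as the number followed, with no allowance for loss before randomisation; the SAP recruits 187 to randomise 168

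*Protocol*

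**What the plan says.** **Protocol.** Only one sample-size figure appears.

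- Resources (e), on recruitment: "We will have access to over 700 qualified patients at VAPAHCS and hope to recruit approximately 168 participants".
- Section 8a, where the form asks how many participants are expected to be enrolled: "we focus on a sample of 168 male and female cannabis dependent adult veterans with sleep disturbances".
- Section 2a, on the design: a "between subjects prospective design to follow 168 Veterans with CUD and co-occurring insomnia over the course of six months".
- Section 8i, on the order of events: "Likely eligible participants will be enrolled in the study and assessed for presence of cannabis use disorder". It then adds: "Participants who are negative for cannabis use disorder or insomnia, will end study participation at this point".

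The protocol mentions neither 187 nor any allowance for loss before randomisation.

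**SAP.** Two figures appear, and they are kept apart.

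- Section 2a.3.d (Participants): "a sample of 187 will provide a final randomization of 168 Veterans into one of the three treatment conditions".
- Missing Data: "First, we will account for 10% loss prior to randomization", and then "we will aim to recruit 187 individuals, with the goal of randomizing 168 individuals for the intent-to-treat analyses".
- Section 2a.3.f (Participant Retention) repeats the 187 and 168, and adds that people who do not complete baseline are replaced.
- Power Analysis: the calculations use 168, or 56 per group.

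**The concern.** In the protocol the same 168 stands at two different points in the participant flow: entry to the study, and the sample followed through the groups. Both can be true only if nobody fails eligibility or drops out at baseline. Section 8i provides for failures, and the SAP expects a 10% loss.

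The SAP's power statements rest on 168 randomised. Its Power Analysis presents 168 as the number required for the mediation test at power .80, so that calculation has no stated slack. If the study team, the ethics board or the data monitoring committee took 168 enrolled as the end of recruitment, the randomised sample would be smaller than the one the SAP was powered on. Follow-up loss would come on top: section 2a.3.f of the SAP expects 80% to complete all follow-up assessments.

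**Working it through.** **Inputs**

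| Input | Value | Source |
|---|---|---|
| Number to recruit or enrol, protocol | 168 (approximate) | Resources (e), 8a |
| Number followed, protocol | 168 | 2a |
| Number to recruit, SAP | 187 | 2a.3.d, 2a.3.f, Missing Data |
| Number randomised, SAP | 168, 56 per group | 2a.3.d, Power Analysis |
| Loss before randomisation | 10% | 2a.3.d, 2a.3.f, Missing Data |
| Conservative sleep effect (Aim 2) | d = .56 | Power Analysis |
| Abstinence, placebo v CBT-I | 20% v 50% | Power Analysis |
| Alpha | .05; two-sided is my assumption | Power Analysis |

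**1. The SAP's own figure.** Recruited = randomised / (1 − loss) = 168 / 0.90 = 186.7, rounded up to 187. Back-check: 187 × 0.90 = 168.3. The SAP's figure reproduces exactly.

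**2. The same loss applied to the protocol's figure.** This assumes that 168 is a ceiling on people entering baseline and that nobody is replaced. Then 168 × 0.90 = 151.2, or about 151 randomised. Per arm, 151.2 / 3 = 50.4, or about 50. That is 168 − 151 = 17 short.

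**3. Other loss rates.** The protocol gives no rate, so this range is assumed.

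| Loss | Randomised out of 168 entering |
|---|---|
| 5% | 159.6, about 160 |
| 10% | 151.2, about 151 |
| 15% | 142.8, about 143 |
| 20% | 134.4, about 134 |

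**4. Pairwise power for d = .56.** Two-sample t-test, no covariate adjustment, noncentrality = d × √(n/2).

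- n = 56 per arm: .56 × √28 = 2.963 on 110 degrees of freedom; power .836.
- n = 50 per arm: .56 × √25 = 2.800 on 98 degrees of freedom; power .792.
- The smallest d detectable with power .80 rises from .534 to .566, just past .56.

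**5. Pairwise power for 20% v 50% abstinence.** Normal approximation, pooled proportion .35, power = Φ[(.30 − 1.96 × SE0) / SE1], with SE0 = √(2 × .35 × .65 / n) and SE1 = √((.16 + .25) / n).

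- n = 56: SE0 = .0901, SE1 = .0856; power .925.
- n = 50: SE0 = .0954, SE1 = .0906; power .894.

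Both stay above the .80 that the SAP claims for this comparison.

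**The case against.** A reader might infer that the approved protocol yields only about 151 randomised participants. The case against that reading is strong, and most of it stands.

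- **No cap is stated.** Resources (e) speaks of a hope and an approximate number. Nowhere is 168 a ceiling or a stopping point, and SAP 2a.3.f replaces baseline non-completers.
- **168 may simply be the randomised target carried over.** Protocol 2a and the SAP's Design Framework describe the 168 followed in almost the same sentence, and in the SAP that figure sits beside 187 recruited. Section 8a also describes people who already have both conditions.
- **Enrolment is used loosely.** Section 8i speaks of enrolling likely eligible people, then of including those who test positive. It is not a formal definition.
- **The 10% may not be the loss in question.** The SAP ties it to attrition around baseline and does not say that it covers failed eligibility, which section 2a.3.g treats separately. It also predates the modification that dropped the motivation criterion and replaced overnight polysomnography with the STOP-Bang.
- **The funded proposal is listed among the protocol's attachments.** The 187 may therefore have been available to the ethics board.
- **The power cost is small.** At the d = 1.4 hypothesised for cannabis use frequency, power is essentially 1 with either 56 or 50 per arm. The d = .56 figures ignore the three covariates in the SAP's calculation.

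These points remove the claim of a certain shortfall. They do not remove the mismatch. If 168 is the randomised target, it is mislabelled in Resources (e) and 8a, which concern recruitment and enrolment. If non-completers are replaced, more than 168 people will be enrolled, and the protocol's figure is again not the enrolment figure. Either way, the protocol body lacks the number that the SAP plans to recruit.

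**Conclusion.** The mismatch is real and should be corrected. The protocol uses 168 for recruitment, expected enrolment and the followed sample, and allows for no loss between them. The SAP needs 187 recruited to reach 168 randomised, a difference of 19 people.

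The documents do not support saying that the trial will randomise only 151. That figure needs three assumptions: 168 is a ceiling at entry to baseline, nobody is replaced, and the SAP's 10% covers all loss before randomisation under the current screening. If all three held, unadjusted pairwise power at d = .56 would drop from .84 to .79, and the abstinence comparison would go from .93 to .89. The effect on the mediation test cannot be computed, because the SAP does not give that calculation's inputs.

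The SAP's own arithmetic is correct. The fault lies in consistency between the documents. It merits an amendment because it concerns the trial's sample size, even though the likely loss of power is modest.

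**What to change.** - In protocol Resources (e) and 8a, state 187 consented or enrolled in order to randomise 168.
- In 1a and 2a, label the 168 as the number randomised.
- Confirm or revise the 10% allowance under the modified screening, and say whether it includes people found ineligible at baseline. If the rate changes, recompute the enrolment figure as 168 / (1 − loss).
- If 168 enrolled is in fact a ceiling, restate the SAP's randomised number and its power to match.

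The cost is one wording amendment to the ethics board. At the 10% allowance it adds no participants beyond the 187 that the SAP already plans, and it gives those monitoring progress distinct enrolment and randomisation targets.
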